#### Secondary objective

Secondary objectives are to compare the effects of CR, PE, EMDR, to WL for researcherrated severity of PTSD symptoms at the separate time-points (i.e. mid-treatment, posttreatment, and at 6-month follow-up) and to test the effects (over time and at each timepoint) for clinician-rated presence of PTSD diagnosis according to the DSM-5 criteria, and self-reported severity of complex PTSD symptoms.

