## Primary Outcome Analysis

To evaluate changes in researcher-rated PTSD symptom severity over time and treatment differences, a LMM will be fitted using restricted maximum likelihood (REML) estimation. The primary model includes baseline scores as covariate, treatment condition as fixed effect, time as categorical variable, an interaction term between treatment condition and time, and a random intercept for each participant to account for within-subject correlations. An interaction effect between treatment condition and time variables would indicate differential treatment effects over time. To appropriately model the within-subject correlation of repeated outcome measures across unequally spaced timepoints, an unstructured covariance matrix will be applied to the residuals in the LMM. This results in the following model equation:

$$Y_{ij} = \beta_0 + \beta_1 \cdot Baseline_i + \sum_{k=1}^{3} \beta_{2k} \cdot Group_{ik} + \sum_{l=1}^{3} \beta_{3l} \cdot Time_{jl} + \sum_{k=1}^{3} \sum_{l=1}^{3} \beta_{4kl} \cdot (Group_{ik} \times Time_{jl}) + u_i + \varepsilon_{ij}$$

Where:

- *Yii*: Outcome for participant *i* at timepoint *j*
- *Baseline*i: Baseline outcome value for participant *i*
- *Groupik*: Dummy-coded treatment condition indicators (3 dummies: CR, PE, EMDR; WL = reference)
- *Timejl*: Dummy-coded time indicators (3 dummies: midtreatment, posttreatment, 6-month follow-up; baseline = reference)
- $Group_{ik} \times Time_{il}$ : Group-by-time interaction terms
- $u_i$ : Random intercept for participant i
- $\varepsilon_{ii}$ : Residual error
- Fixed effects:
  - Intercept  $\beta_0$ : Mean outcome at baseline for WL
  - $\circ$   $\beta_1$ : Effect of individual baseline outcome value (covariate)
  - $\circ$   $\beta_{2k}$ : Group main effects at baseline, compared to WL
  - $\circ$   $\beta_{3l}$ : Time effects for WL (how outcomes change over time within WL)
  - $\circ$   $\beta_{4kl}$ : Additional group-specific changes over time relative to WL

To quantify the magnitude of treatment effects, effect sizes will be estimated for timepoints T3 and T6 based on the mean pre-post change (i.e. baseline scores vs. follow-up scores) of the treatment condition minus the mean pre-post change of WL, divided by the pooled pretest standard deviation 

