## Secondary and Tertiary Outcome Analyses

For continuous outcomes, LMMs with similar methodology as the primary outcome analysis will be applied. For dichotomous outcomes (e.g., clinician-rated presence of PTSD diagnosis) generalized linear mixed models (GLMMs) with a logit link function will be used, in line with the following model equation:

$$\log\left(\frac{\Pr(Y_{ij}=1)}{1-\Pr(Y_{ij}=1)}\right) = \beta_0 + \beta_1 \cdot Baseline_i + \sum_{k=1}^3 \beta_{2k} \cdot Group_{ik} + \sum_{l=1}^3 \beta_{3l} \cdot Time_{jl} + \sum_{k=1}^3 \sum_{l=1}^3 \beta_{4kl} \cdot (Group_{ik} \times Time_{jl}) + u_i + \varepsilon_{ij}$$

Here, the left-hand side of the model equation indicates the log-odds of the outcome being 1 (e.g., no longer meeting PTSD diagnosis criteria).

The trial protocol specified Generalised Estimating Equations (GEE) would be used to analyse dichotomous outcomes. This plan has been updated to employ GLMMs, as they allow explicit modeling of random effects and individual-level variability, while offering more robust performance when handling missing data under missing at random (MAR) assumptions, which better suits our study's anticipated data structure.

Similar to the primary analysis, effect size of continuous outcomes will be estimated with  $d_{ppc2}$ . For dichotomous outcomes, odds ratios (ORs) will be calculated from the fitted GLMM. Here, exponentiated model coefficients will be interpreted as odds ratios comparing the odds of the outcome between treatment arms and timepoints.

In addition to testing treatment effect on primary and secondary outcomes over time, post-hoc pairwise comparisons between treatment groups and the waitlist control group will be conducted at each timepoint using estimated marginal means with Bonferroni correction to adjust for multiple comparisons.

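### The reported odds ratio for PTSD diagnosis is tied to single GLMM coefficients, which do not give a usable therapy-versus-WL odds ratio at each follow-up visit; the logit-scale marginal-means contrast should be named instead

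*SAP*

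**What the plan says.** The Secondary objective section sets out "to test the effects (over time and at each timepoint) for clinician-rated presence of PTSD diagnosis". For dichotomous outcomes, the Secondary and Tertiary Outcome Analyses section states that "generalized linear mixed models (GLMMs) with a logit link function will be used". Its equation has a baseline covariate, group, time, group-by-time and a participant random intercept. Odds ratios are to be calculated from that fit, and "exponentiated model coefficients will be interpreted as odds ratios comparing the odds of the outcome between treatment arms and timepoints".

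The terms are defined in Primary Outcome Analysis:

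- Group: "3 dummies: CR, PE, EMDR; WL = reference".
- Time: "3 dummies: midtreatment, posttreatment, 6-month follow-up; baseline = reference".
- β2k: "Group main effects at baseline, compared to WL".
- β4kl: "Additional group-specific changes over time relative to WL".

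Two further statements in the secondary section matter here. The protocol had specified GEE, and "This plan has been updated to employ GLMMs". The paragraph after the odds-ratio rule then adds Bonferroni-corrected comparisons of each therapy with WL at each timepoint, based on estimated marginal means, for primary and secondary outcomes.

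**The concern.** The objective needs a therapy-versus-WL effect on diagnosis at each visit. The only rule that defines the reported odds ratio points to exponentiated coefficients, without saying which coefficient or which combination. Under the printed coding, neither the group coefficient nor the interaction coefficient is that effect by definition. Diagnosis is also a special case, because almost nobody can be free of PTSD at the reference time. An analyst following the rule literally could report an unstable number, or a ratio of odds ratios, as the arm effect. The significance test beside it would come from a different quantity, the marginal-means contrast.

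There is a second, smaller matter. Replacing GEE with a GLMM changes the odds ratio from population-averaged to subject-specific, and the SAP does not say so.

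**Working it through.** **Inputs from the SAP.** Model and coding are as quoted. From Sample Size Calculation: 50 per arm and 20% attrition. That figure is the SAP's only computed one, and it reproduces: 2 × ((1.96 + 0.84)/0.5)² × (1 + 2 × 0.45)/3 = 39.8, rounded up to 40, and 40/0.80 = 50. The point does not depend on it; it only supplies 40 analysed per arm for the illustration.

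**Inputs assumed.** Remission in WL of 5, 8 and 10 of 40 at T2, T3 and T6, and in a therapy arm of 10, 18 and 20 of 40. Nobody is in remission at baseline, which is inferred from the description of the population in the Introduction.

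**Step 1: what each coefficient is.** For therapy k at visit l, with baseline and WL as references:

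- log-odds in WL at baseline: β0, plus the covariate term
- therapy minus WL at baseline: β2k
- visit l minus baseline within WL: β3l
- therapy minus WL at visit l: β2k + β4kl

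So exp(β2k) is a baseline odds ratio, exp(β3l) is a time odds ratio within WL, and exp(β4kl) is a ratio of two odds ratios. The quantity wanted is exp(β2k + β4kl).

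**Step 2: printed coding, baseline rows included.** The true T6 odds ratio is (20/20)/(10/30) = 3.00. A logistic fit of the printed design, omitting the random intercept and the baseline covariate, gave:

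| Iterations | β0 | SE of β4 (T6) | exp(β2 + β4) |
|---|---|---|---|
| 5 | −6.56 | 3.7 | 3.00 |
| 10 | −11.57 | 44.0 | 3.00 |
| 15 | −16.57 | 536.6 | 3.00 |
| 25 | −26.57 | 79,631.7 | 3.00 |

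The point estimate of β4 was 1.099 = log 3 throughout, because both arms were equally empty at baseline. Its standard error has no limit, so no interval or test can be attached to it. The T6 contrast has an ordinary standard error: √(1/20 + 1/20 + 1/10 + 1/30) = 0.483. Its 95% CI is exp(1.099 ± 1.96 × 0.483) = 1.16 to 7.73.

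**Step 3: nearly constant baseline.** Suppose one therapy participant and no WL participant lacks the diagnosis at baseline, and add one half to each baseline cell. Then exp(β2) = (1.5/39.5)/(0.5/40.5) = 3.08 and exp(β4) = 3.00/3.076 = 0.98. With the arms swapped, they are 0.33 and 3.00 × 3.076 = 9.23. The T6 odds ratio is 3.00 in both cases.

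**Step 4: baseline rows dropped.** The 16 columns of the design, without the baseline covariate, then have rank 12, so a new reference visit has to be chosen. With T2 as reference, exp(β2) = (10/30)/(5/35) = 2.33, which is the odds ratio at T2 only. For T6, exp(β4) = 3.00/2.33 = 1.29, which shows only how the effect differs from T2. The T6 odds ratio is 2.33 × 1.29 = 3.00.

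**Step 5: conditional and marginal odds ratios.** Let p(η) be the average of expit(η + s·z) over standard normal z. Assume 25% remission in WL and a conditional odds ratio of 3. Choose η so that p(η) = 0.25; the therapy proportion is then p(η + log 3).

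| Random-intercept SD (s) | 0 | 1 | 1.5 | 2 | 3 |
|---|---|---|---|---|---|
| Therapy proportion | 0.500 | 0.455 | 0.424 | 0.398 | 0.360 |
| Marginal odds ratio | 3.00 | 2.51 | 2.21 | 1.98 | 1.69 |

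**The case against.** The strongest reply is that the right quantity is already in the plan. The marginal-means comparisons with WL at each timepoint cover secondary outcomes, and on the logit scale they equal β2k + β4kl. The rule can also be read generously: the odds ratios are calculated from the fitted model, which does not exclude combinations of coefficients, and a comparison across both arms and timepoints may describe the interaction. The coefficient definitions in Primary Outcome Analysis are themselves correct.

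Most of this stands. A reader might infer that the effect on diagnosis will certainly be misreported; the documents do not support that. What remains is that the marginal-means comparisons are introduced as additional post-hoc tests, with no scale given and no link to the reported odds ratio.

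A reader might also infer that a real effect present at every visit would appear as an odds ratio of 1. That requires a post-baseline reference visit, which is not the printed coding. Under the printed coding with arms equal at baseline, β2k is 0 and exp(β4kl) equals the visit odds ratio as a point value. The difficulty there is estimability, as Step 2 shows.

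Finally, a subject-specific odds ratio is a valid estimand, and the change of method is declared with reasons. A reader might infer that the plan passes it off as a population effect. The SAP never calls it a population or average comparison, so Step 5 supports a request for a label and nothing more.

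**Conclusion.** The rule that defines the reported odds ratio is wrong as written for PTSD diagnosis. With baseline as reference, the single coefficients rest on an outcome that is nearly constant at baseline. In the illustration, β4 had an unbounded standard error, against 0.483 for the T6 contrast. If baseline rows are dropped, one coefficient describes the new reference visit and the others only describe departures from it. In either case the reported odds ratio and its interval could differ from the quantity tested.

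The algebra in Step 1 needs no assumption beyond the SAP's own coding. The estimability problem rests on participants having PTSD at entry, which is inferred from the described population. The sizes shown rest on assumed remission counts, 40 analysed per arm, and a fit without the random intercept or baseline covariate.

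The change from a marginal to a conditional odds ratio is a matter of labelling. Its direction is certain whenever the random-intercept variance is above zero, but its size is unknown from the SAP.

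**What to change.** Replace the sentence on exponentiated coefficients in Secondary and Tertiary Outcome Analyses with wording to this effect:

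*For PTSD diagnosis, the odds ratio for each therapy against WL at T2, T3 and T6 will be the exponentiated contrast of estimated marginal means on the logit scale, with 95% CI, from a model fitted to post-baseline visits only. It is conditional on the participant random intercept (subject-specific).*

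The same contrast should be named as the one tested at each visit.

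State one coding direction as well. The section names the outcome as presence of the diagnosis, but its example codes absence of the diagnosis as 1. The two directions give reciprocal odds ratios, for example 3.00 and 0.33.

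Model-standardised proportions and risk differences per arm and visit, averaged over the random intercept, would help readers and ease comparison with the GEE result first planned. They are an optional addition and correct no error.

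The cost is one replaced sentence and a few lines of R, with no new data. Leaving baseline rows out of the diagnosis model loses almost nothing, because they hardly vary.

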## Sample Size Calculation

A formal power analysis was conducted to determine the required sample size for the planned longitudinal intention-to-treat (ITT) analyses using linear mixed models (LMM).

Based on data from previous randomized controlled trials in this field , the calculation used the following parameters: significance level ( $\alpha$ ) of 0.05 (two-sided), power (1- $\beta$ ) of 0.80, expected correlation between repeated measures ( $\rho$ ) of 0.45, and 3 repeated follow-up assessments. The minimum detectable effect size was set at 0.5 (medium effect, compared to waiting list control), while accounting for an anticipated attrition rate of 20%. These calculations indicated that 50 participants would be needed in each study arm. Therefore, our aim will be to randomize a total of 200 participants.

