## **Statistical Methods**

## General principles

This Statistical Analysis Plan describes the methods for analysis of the effect of traumafocused therapies for individuals with PTSD and psychosis on primary, secondary, and adverse outcomes. Other analyses outlined in the published protocol, such as costeffectiveness analysis, will be described and published separately.

All analyses will be completed in R (version 4.4.2) unless stated otherwise. All tests are two-sided and a significance level of  $\alpha$ =0.05 is adopted.

Data will be analysed following the intention-to-treat principle, ensuring all randomized participants are analysed in their assigned groups, regardless of adherence or missing data. Missing data will be treated as missing at random.

Statistical analyses will be carried out by [name], under supervision of dr. [name], dr. [name], dr. [name], and prof. dr. [name]. An independent statistician will be consulted throughout the analysis process.

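### Plain Bonferroni for the per-visit therapy-versus-waitlist contrasts is valid, but Holm or a Dunnett-type adjustment over the same, explicitly stated family is more powerful

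*SAP*

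**What the plan says.** The multiplicity rule is one sentence at the end of Secondary and Tertiary Outcome Analyses. Pairwise comparisons of the therapy arms with WL, for primary and secondary outcomes, "will be conducted at each timepoint using estimated marginal means with Bonferroni correction to adjust for multiple comparisons". The number of tests that the correction covers is not given.

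The comparisons serve the Secondary objective, which asks for effects "at the separate time-points (i.e. mid-treatment, posttreatment, and at 6-month follow-up". That makes three post-baseline visits, each with three contrasts: CR, PE and EMDR against WL. In the model under Primary Outcome Analysis, time is coded as "3 dummies: midtreatment, posttreatment, 6-month follow-up; baseline = reference".

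Under Sample Size Calculation, the effect size is fixed thus: "The minimum detectable effect size was set at 0.5 (medium effect, compared to waiting list control". The correlation and number of visits are "of 0.45, and 3 repeated follow-up assessments", with two-sided alpha 0.05, power 0.80, 20% attrition and 50 per arm. No multiplicity allowance is mentioned. Allocation is 1:1:1:1 (Randomisation and Blinding).

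**The concern.** The three contrasts at a visit share one control arm. With equal arms and equal variances, any two of them correlate 0.5. Bonferroni ignores this, and it also tests every contrast at the strictest threshold, even after another contrast has been rejected. Both features give away power that standard procedures keep while guaranteeing the same 5% bound on family-wise error over the same contrasts.

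These contrasts are a named secondary objective. They will be read as showing which therapy beats WL at mid-treatment, post-treatment and six months. The sample size was not set for them (see the working), so avoidable loss of power matters. Because the family is unnamed, a reader also cannot tell whether error is meant to be controlled within a visit or across all visits.

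**Working it through.** **1. The plan's own figure.** Take the mean of m = 3 follow-ups with ρ = 0.45 and compound symmetry:

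- variance factor = (1 + 2 × 0.45)/3 = 0.6333
- n = 2 × (1.960 + 0.842)² × 0.6333 / 0.5² = 39.8, so 40 evaluable per arm
- 40 / 0.80 = 50 per arm, which matches the plan exactly

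The stated 50 per arm therefore corresponds to one test at 0.05 of the three-visit average per therapy, without multiplicity or baseline adjustment. For a single visit without baseline adjustment, the same formula with variance factor 1 gives 62.8, so 63 evaluable and 79 randomised per arm.

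**2. Inputs for a single-visit contrast.** From the SAP: two-sided alpha 0.05, ρ = 0.45, and 50 × 0.80 = 40 evaluable per arm. Assumed: d = 0.5 at each visit (the SAP does not tie its 0.5 to a visit), normal theory, equal variances, contrast correlation 0.5, and a variance factor of 1 − 0.45² = 0.7975 for baseline adjustment. Results with factor 1 (no baseline adjustment) are given alongside.

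- Noncentrality, adjusted: 0.5 × √(40 / (2 × 0.7975)) = 2.504
- Noncentrality, unadjusted: 0.5 × √(40 / 2) = 2.236

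**3. Bonferroni over three.** The critical value is 2.394 (threshold 0.05/3 = 0.0167). Power per contrast is Φ(2.504 − 2.394) = 54.4% adjusted and Φ(2.236 − 2.394) = 43.7% unadjusted, however many therapies work.

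**4. Alternatives over the same three contrasts.** Simulation with 1,000,000 draws. Step-down Dunnett uses critical values 2.349, 2.212 and 1.960. Average power per effective therapy:

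| Therapies that work | Bonferroni, adj. / unadj. | Holm, adj. / unadj. | Step-down Dunnett, adj. / unadj. |
|---|---|---|---|
| three | 54.4% / 43.7% | 62.0% / 50.5% | 63.1% / 51.8% |
| two | 54.4% / 43.7% | 57.5% / 46.5% | 59.0% / 48.1% |
| one | 54.4% / 43.7% | 54.5% / 43.7% | 56.3% / 45.5% |

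Single-step Dunnett (critical value 2.349), the natural source of simultaneous intervals, has about 56% power (adjusted) in every row.

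**5. Error within a visit.** With no therapy effective, family-wise error is 4.4% for Bonferroni and Holm and 5.0% for step-down Dunnett. With one or two effective therapies it is lower for all three methods.

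**6. If the family is all nine contrasts.** Three visits × three contrasts gives a threshold of 0.05/9 = 0.0056 and a critical value of 2.773. With all therapies effective at all visits and correlation 0.45 between visits:

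| Method over nine | Power, adj. | Power, unadj. |
|---|---|---|
| Bonferroni | 39.4% | 29.6% |
| Holm | 48.4% | 36.2% |

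Under the global null, error over the nine contrasts is 4.3% with Bonferroni over nine, 11.8% with Bonferroni over three at each visit, and 13.1% with Dunnett at each visit. Holm has the same global-null error as Bonferroni over the same family, because its first step is the same test.

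**The case against.** **Bonferroni is valid.** It controls error, needs no assumption about correlation, and gives adjusted p values and simultaneous intervals that agree. The SAP calls these comparisons post hoc, and they are secondary. All of this stands. The point is lost efficiency, not loss of type I error control.

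**The gain depends on the truth.** The 8 to 9 points (adjusted) need all three therapies to work equally. With one effective therapy, Holm adds less than 0.1 point and step-down Dunnett about 2. This also stands.

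**Dunnett's correlation of 0.5 is not general.** It follows from equal arms and variances. For PTSD diagnosis, analysed with a logit mixed model, it varies with event rates and attrition. This stands, and it is why the correlations should come from the fitted model. Holm does not depend on them.

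**A reader might infer that the fix recovers, at no cost in error, the drop from 54% to 39% that comes with a nine-test correction.** It does not. Most of the difference between Bonferroni over nine and Holm over three comes from shrinking the family, and error over the nine contrasts rises from about 4% to 12–13%. The fair comparisons are three against three, or nine against nine.

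**A reader might also infer a family of twelve,** since baseline is a level of time in the model. The Secondary objective lists only the three post-baseline visits, and a reference level in a model does not show that baseline contrasts will be tested. The most natural reading of the sentence is three contrasts per visit.

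**Conclusion.** The point holds as a cheap improvement to a secondary analysis. Over the three contrasts at a visit, Bonferroni gives 54% power per contrast. Holm gives between 54% and 62%, and step-down Dunnett between 56% and 63%, depending on how many therapies work. Without baseline adjustment the corresponding figures are 44%, 44% to 51%, and 46% to 52%. All three methods keep per-visit family-wise error at or below 5%.

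The size rests on d = 0.5 at the visit, 40 evaluable per arm, equal variances and the assumed variance factor. The ordering does not: over a given family Holm never rejects less than Bonferroni, and step-down Dunnett with the correct correlations never rejects less than Holm.

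The documents do not support calling the planned correction an error. Nor do they support a claim about the primary over-time analysis, which this correction does not touch.

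**What to change.** Replace the Bonferroni clause by text to this effect:

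- For each primary and secondary outcome, the family is the three therapy-versus-WL contrasts at each post-baseline visit (T2, T3, T6). Family-wise error is controlled at 5% per visit, and not across visits.
- P values are adjusted by Holm, or by step-down Dunnett using the contrast correlations estimated by the model.
- Single-step Dunnett simultaneous 95% confidence intervals are reported from the same estimated marginal means.

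If control over all nine contrasts is intended, say so and use Holm over nine (about 48% against 39% for Bonferroni, adjusted, if all therapies work at all visits).

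The cost is a sentence or two in the SAP and a changed adjustment option in R, with no new data or model. There are two small downsides. Step-down p values will not always agree with the simultaneous intervals, which are nevertheless slightly narrower than Bonferroni's (2.349 against 2.394). Per-visit families leave error across visits uncontrolled, which the text should state openly.
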